Subjects will undergo a screening visit to confirm eligibility requirements. Baseline/day 1 visit should not occur prior to confirmation of subject's SLE-related eligibility by the adjudication team and must occur up to 33 days from the screening visit. At baseline/day 1 visit, prior to randomization, the subject must present with disease activity (defined by clinical hSLEDAI score ≥ 4) and stability and compliance with OCS and other immunosuppressant/immunomodulator doses (by reviewing medication history). Subjects may be randomized at any time after confirmation of all eligibility criteria, but the maximum time between initiation of screening and randomization is 33 days. Subjects who do not meet all the eligibility requirements at the baseline/day 1 visit will be considered screen failures. Subjects may be allowed to rescreen as detailed in Section 9.1.1.

After randomization, adjudication reviews will be completed throughout the study period on blinded endpoint data from enrollment to week 52 for all randomized subjects and for all visits. This includes review of all efficacy-related endpoint data.

Immunosuppressant/immunomodulator dose should remain stable through week 52. For OCS, initiation of, or temporary increases in OCS are allowed from weeks 0 to 8, provided that return to baseline dose occur within the subsequent 2 weeks, as outlined in Section 7.1.4.2. OCS can be tapered at the investigator's discretion but shall not be changed during the last 8 weeks (week 44 to 52) of the 52-week treatment period.

Subjects listed below will be allowed to continue the study but will be considered treatment failures for primary efficacy endpoint analyses for the subsequent time points. **These subjects will also be allowed to continue investigational product at the investigator's discretion, except subjects who initiate any immunosuppressant/immunomodulator listed in Section 7.1.7 (treatments a through i).**

- Subjects requiring initiation or increase in OCS dose > 5 mg/day (prednisone or equivalent), **or intramuscular (IM) CS or intravenous (IV) CS** at any time point during the study, subjects requiring initiation or increase in OCS dose ≤ 5 mg/day (prednisone or equivalent) after week 10, or subjects requiring initiation or increase in OCS dose ≤ 5 mg/day (prednisone or equivalent) from week 0 to week 8 who cannot return to their baseline dose within the following 2 weeks (Section 7.1.4.2).

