7.1.7 Excluded Treatments, Medical Devices, and/or Procedures During Study Period

Subjects who are receiving treatments listed below are allowed to remain in the study at the investigator's discretion. Subjects are also allowed to continue investigational product at the investigator's discretion except those who initiate any treatment listed below from a through i:

- a. investigational therapies or commercially available biologic agents **with immunosuppressive/immunomodulatory activity** for SLE or other conditions (eg, rituximab or belimumab)
- b. cytotoxic agents including: chlorambucil, cyclophosphamide, nitrogen mustard, or other alkylating agents
- c. **thalidomide**
- d. sirolimus
- e. oral calcineurin inhibitors (eg, tacrolimus, cyclosporine, etc.)
- f. T cell depleting agents (eg, antithymocyte globulin, Campath)
- g. recombinant IL-2 (eg, Proleukin)
- h. **JAK inhibitors**
- i. **live vaccines**
- j. intra-articular, **IM**, or **IV CS**, including adrenocorticotropic hormone
- k. intra-articular hyaluronic acid injections

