9.2.2.2 British Isles Lupus Assessment Group Index

The **British Isles Lupus Assessment Group (BILAG)** index (BILAG 2004) evaluates disease activity in 9 separate organ systems and comprises a total of 97 items. Each item is measured qualitatively by review of medical history and physical examination (yes/no, improving/same/worse/new) or quantitatively by measuring laboratory values. Based on these items, each of the 9 organ systems allocated an alphabetical score of A (most active), B (moderate activity), C (minor activity), D (**no activity**) or E (never present). BILAG descriptors will be scored based on a review of medical history, physical examination, and clinical laboratory findings. Findings should reflect activity during the 4-week period prior to the current visit and should be related to the subject's SLE.

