9.2.2.12 BICLA Index Response

The BICLA response is defined as at least 1 gradation of improvement in baseline BILAG domain scores in all body systems with moderate or severe disease activity at entry (eg, all A [severe disease] domain scores falling to B [moderate], C [mild], or D [no activity], and all B domain scores falling to C or D); no new BILAG 2004 A domain score and no > 1 new BILAG 2004 B domain scores compared with baseline; **no worsening of the hSLEDAI score from baseline; no \geq 0.3-point deterioration from baseline in PGA (scale 0 to 3); and no use of more than protocol-allowed therapies (ie, initiation or increase in OCS dose > 5 mg/day prednisone [or equivalent] or IM CS or IV CS at any time point during the study; initiation or increase in OCS dose ≤ 5 mg/day prednisone [or equivalent] after week 10; initiation or increase in OCS dose ≤ 5 mg/day prednisone [or equivalent] between week 0 and week 8 that was not returned to baseline dose within the following 2 weeks; increase in current or initiation of new immunosuppressant/immunomodulator(s) at any time during the study); and no initiation of non-protocol treatment for SLE** (Wallace et al, 2011; Wallace et al, 2014).

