Systemic Lupus Erythematosus Responder Index (SRI-4)

A subject achieves SRI-4 response if all of the following criteria are met:

1. ≥ 4 -point reduction from baseline in hSLEDAI score
2. no new BILAG 2004 A and no > 1 new BILAG 2004 B domain scores compared with baseline (e.g. no B, C, D or E scores at baseline becomes A or no more than 1 C, D or E score at baseline becomes B)
3. and < 0.3 -point deterioration from baseline in PGA (scale 0 to 3).
4. no use of more than protocol-allowed therapies (i.e. initiation or increase from baseline in oral corticosteroid (OCS) dose > 5 mg/day (prednisone or equivalent) or intravenous (IV) or intramuscular (IM) at any time point during the study; initiation or increase in OCS dose ≤ 5 mg/day (prednisone or equivalent) after week 10; initiation or increase in OCS dose ≤ 5 mg/day (prednisone or equivalent) between week 0 and week 8 that was not returned to baseline dose within the following 2 weeks; initiation or increase from baseline of immunosuppressant/immunomodulator(s) at any time during the study.)

The latest visit date among hSLEDAI, BILAG and PGA will be considered the SRI-4 visit date. In the case when all three visit dates are missing, the upper limit of the analytic window of this visit will be the SRI-4 visit date.

BILAG-based Composite Lupus Assessment (BICLA)

A subject achieves BICLA response if all of the following criteria are met:

1. at least one gradation of improvement in baseline BILAG domain scores in all body systems with moderate or severe disease activity at entry (e.g., all A (severe disease) domain scores at baseline falling to B (moderate), C (mild), or D (no activity), and all B domain scores at baseline falling to C or D)
2. no new BILAG 2004 A domain score and no > 1 new BILAG 2004 B domain scores compared with baseline
3. no worsening of the hSLEDAI score from baseline
4. < 0.3-point deterioration from baseline in PGA (scale 0 to 3)

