5. and no use of more than protocol-allowed therapies (i.e. initiation or increase from baseline in oral corticosteroid (OCS) dose > 5 mg/day (prednisone or equivalent) or intravenous (IV) or intramuscular (IM) at any time point during the study; initiation or increase in OCS dose ≤ 5 mg/day (prednisone or equivalent) after week 10; initiation or increase in OCS dose ≤ 5 mg/day (prednisone or equivalent) between week 0 and week 8 that was not returned to baseline dose within the following 2 weeks; initiation **or increase from baseline** of immunosuppressant/immunomodulator(s) at any time during the study.

Swollen and Tender Joint Count

Joints that have been replaced during the study, or have suffered trauma or received intra-articular injections, are considered non-evaluable.

Swollen Joint Count Assessments – A total 28 joints will be scored for presence or absence of swelling. A separated score for joints in the hands and wrists will be calculated.

Tender Joint Count Assessments – A total 28 joints will be scored for presence or absence of tenderness. A separated score for joints in the hands and wrists will be calculated.

Swollen and Tender Joint Count Assessments: joints in hands and wrists will be scored for the simultaneous presence of absence of swelling and tenderness.

Cutaneous Lupus Erythematosus Area and Severity Index (CLASI)

The CLASI consists of 2 scores, the first summarizes the activity of the disease while the second is a measure of the damage done by the disease. Activity is scored based on erythema, scale/hyperkeratosis, mucous membrane involvement, acute hair loss and non-scarring alopecia. Damage is scored in terms of dyspigmentation and scarring, including scarring alopecia. Subjects are asked whether dyspigmentation due to cutaneous lupus lesion usually remains visible for more than 12 months, which is taken to be permanent. If so, the dyspigmentation score is doubled. The scores are calculated by simple addition based on the extent of the symptoms. The CLASI is designed as a table where the rows denote anatomical areas, while the columns score major clinical symptoms. The extent of involvement for each of the skin symptoms is documented according to specific anatomic areas that are scored according to the worst affected lesion within that area for each symptom.

A CLASI response is defined as $\geq 50\%$ improvement of CLASI activity score from baseline.

Lupus Low Disease Activity State (LLDAS)

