A	Severe disease activity requiring any of the following treatment: 1. systemic high dose oral glucocorticoids (equivalent to prednisolone > 20 mg/day) 2. intravenous pulse glucocorticoids (equivalent to pulse methylprednisolone \geq 500 mg) 3. systemic immunomodulators (include biologicals, immunoglobulins and plasmapheresis) 4. therapeutic high dose anticoagulation in the presence of high dose steroids or immunomodulators e.g.: warfarin with target INR 3 - 4
B	Moderate disease activity requiring any of the following treatment: 1. systemic low dose oral glucocorticoids (equivalent to prednisolone \leq 20 mg/day) 2. intramuscular or intra-articular or soft tissue glucocorticoids injection (equivalent to methylprednisolone < 500mg) 3. topical glucocorticoids 4. topical immunomodulators 5. antimalarials or thalidomide or prasterone or acitretin 6. symptomatic therapy e.g.: NSAIDs for inflammatory arthritis
C	Mild disease
D	Inactive disease but previously affected
E	System never involved

BILAG Constitutional Scoring Algorithm

Grade	Criteria
A	1. Pyrexia recorded as 2 (same), 3 (worse) or 4 (new) AND 2. Any 2 or more of the following recorded as 2 (same), 3 (worse) or 4 (new): a) Weight loss b) Lymphadenopathy/splenomegaly c) Anorexia
B	1. Pyrexia recorded as 2 (same), 3 (worse) or 4 (new) OR 2. Any 2 or more of the following recorded as 2 (same), 3 (worse) or 4 (new): a) Weight loss b) Lymphadenopathy/splenomegaly

	c) 3. BUT do not fulfil criteria for Category A
C	1. Pyrexia recorded as 1 (improving) OR 2. One or more of the following recorded as > 0: a) Weight loss b) Lymphadenopathy/Splenomegaly c) Anorexia 3. BUT does not fulfil criteria for category A or B
D	Previous involvement (i.e. A, B, C or D domain grade at any previous visits or domain previous involvement is yes)
E	No previous involvement
Missing	

BILAG Mucocutaneous Scoring Algorithm

Grade	Criteria
A	Any of the following recorded as 2 (same), 3 (worse) or 4 (new): a) Skin eruption - severe b) Angio-oedema - severe c) Mucosal ulceration - severe d) Panniculitis/Bullous lupus - severe e) Major cutaneous vasculitis/thrombosis
B	1. Any Category A features recorded as 1 (improving) OR 2. Any of the following recorded as 2 (same), 3 (worse) or 4 (new): 1. Skin eruption - mild 2. Panniculitis/Bullous lupus - mild 3. Digital infarcts or nodular vasculitis 4. Alopecia - severe

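### SAP 5.6 drops, without declaring it, the protocol's last BICLA condition, which rules out starting SLE treatment outside the protocol

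*SAP*

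**What the plan says.** BICLA response at week 24 and at week 52 are both secondary endpoints (Protocol 4.1; SAP 2.1).

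Protocol 9.2.2.12 builds the definition from BILAG improvement, no important new BILAG activity, no worsening of hSLEDAI or PGA, and a treatment limit. That limit is spelled out in a bracketed list: oral corticosteroid beyond stated doses and times, intramuscular or intravenous corticosteroid, and a new or increased immunosuppressant or immunomodulator. After the bracket closes, the sentence adds one more condition: "no initiation of non-protocol treatment for SLE".

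SAP 5.6 opens its version with "A subject achieves BICLA response if all of the following criteria are met" and numbers five criteria. The fifth begins "and no use of more than protocol-allowed therapies" and gives the same kind of list. There is no sixth. SAP Section 1 says that the SAP details the analyses of protocol Amendment 3, the version that contains the extra condition.

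**The concern.** A secondary endpoint is defined in one way in the protocol and in a looser way in the document that will be programmed. A subject who meets all five SAP criteria but starts an SLE treatment that the protocol clause excludes would be a non-responder by protocol and a responder in the output. A reader of the report would take the BICLA percentage to follow the protocol definition, since the SAP nowhere says otherwise.

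The clause cannot simply be dismissed as a repetition. The protocol's SRI-4 definition (9.2.2.11) carries the same treatment list and stops there; only BICLA goes further. In the SAP, the treatment criterion for BICLA is nearly the same as the one for SRI-4. The wording may have been carried across from SRI-4, but that is an inference.

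**Working it through.** No figure in the plan depends on this point, so the check is a comparison of texts followed by a logical one.

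**Step 1. Conditions side by side.**

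| Protocol 9.2.2.12 | SAP 5.6 |
|---|---|
| 1. Every baseline BILAG A or B domain improves by a grade or more | Criterion 1 |
| 2. No new BILAG A and at most one new B | Criterion 2 |
| 3. hSLEDAI not worse than baseline | Criterion 3 |
| 4. PGA not worse by 0.3 or more | Criterion 4 |
| 5. Treatment limits (oral, IM and IV corticosteroid; immunosuppressant/immunomodulator) | Criterion 5 |
| 6. "no initiation of non-protocol treatment for SLE" | None |

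**Step 2. Is the clause restored or its removal declared elsewhere in the SAP?**

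- Section 8.3 evaluates BICLA on observed and imputed PGA, hSLEDAI and BILAG. It adds no treatment rule.
- Table 9-2 gives only the summary method.
- Appendix B covers instrument scoring and LLDAS, and adds no BICLA treatment rule.
- Section 10 lists three changes: later interim analyses, some exploratory endpoints, and statistical comparisons. None concerns BICLA.

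**Step 3. Direction.** Treat each condition as met or not met, which gives 2^6 = 64 patterns. The protocol responder needs all six; the SAP responder needs the first five.

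- Protocol responder but SAP non-responder: 0 patterns.
- SAP responder but protocol non-responder: 1 pattern (1 to 5 met, 6 failed).

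So the omission alone can only keep or enlarge the responder set. This holds with conditions 1 to 5 read identically in both documents. It is not a statement about the whole SAP definition. SAP criterion 5 also words the immunosuppressant part a little differently, without the protocol's restriction of initiation to new agents; read literally, that difference can work the other way.

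**Step 4. What can fall into that one pattern?** Criterion 5 already fails a subject for oral corticosteroid beyond the limits, for IM or IV corticosteroid, and for any start or increase of an immunosuppressant or immunomodulator. What remains are treatments outside that list that are given for SLE. The protocol restricts several:

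- intra-articular corticosteroid (7.1.7, item j), where the section says "Subjects who are receiving treatments listed below are allowed to remain in the study";
- topical corticosteroids and calcineurin inhibitors (7.1.4.3);
- NSAIDs and other analgesics (7.1.4.4);
- anti-proteinuria agents started for SLE proteinuria (7.1.4.5).

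Intra-articular hyaluronic acid (7.1.7, item k) is also outside criterion 5, but the documents do not identify it as an SLE treatment. Neither document says which of these the clause covers, and neither gives a rate of use. The size of any increase cannot be computed.

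**The case against.** The strongest reply is that the clause may have no practical content. The protocol never defines the term. The most obvious candidate, intra-articular corticosteroid, runs against the protocol's own pattern: wherever it lists corticosteroid use that makes a subject a failure (5.1, 7.1.4.2, 9.2.2.11, and the list inside 9.2.2.12 itself), it names the IM and IV routes and leaves out intra-articular. Its stated efficacy rule for such injections works through joint counts (Protocol 9.2.2.5). The SAP repeats it: joints that "have suffered trauma or received intra-articular injections, are considered non-evaluable". In addition, SAP Section 10 presents its list as key changes and so does not claim to be complete, and after the futility stop nothing is tested.

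Most of this stands. It shows that no affected subject has been established and that the consequence is small. It does not make the two definitions agree, and it does not show that the sponsor decided to remove the clause.

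Two stronger readings are tempting and are not supported:

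- A reader might infer that a subject given an intra-articular steroid for lupus arthritis is certainly misclassified. With the term undefined and the pattern just described, the documents leave that open.
- A reader might infer the opposite, that BILAG would catch such a subject anyway, because the category B description in SAP Appendix B mentions "intramuscular or intra-articular or soft tissue glucocorticoids injection". That table states the treatment-intention principle behind the categories. The domain grades come from the item algorithms, and the musculoskeletal one uses recorded myositis, arthritis and related symptoms, with no treatment input. An injection does not itself produce a B.

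**Conclusion.** The point holds in a limited form. SAP 5.6 omits a separate condition of the protocol's BICLA definition and does not declare it. With the other criteria held the same, the effect is to keep or enlarge the responder set. The number of subjects affected is unknown and may be zero. Table 9-2 reports BICLA only as number and percentage by arm, no comparison depends on it, and SRI-4 is untouched because its protocol definition has no such clause. This is a minor correction.

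A reader might infer that reported BICLA rates are materially inflated, or look for a ceiling on the effect per subject. The documents support neither. They give no rate of such treatment. The 25% placebo allocation and the 200-subject trigger of the sixth interim analysis give only an expected placebo count (0.25 × 200 = 50), not a guaranteed minimum, so no upper bound in percentage points follows.

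**What to change.** Restore the clause as BICLA criterion 6 in SAP 5.6. The sponsor should state which SLE-indicated treatments outside criterion 5 count, with a yes or no for each of:

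- intra-articular corticosteroid;
- topical agents (Protocol 7.1.4.3);
- NSAIDs and analgesics (7.1.4.4);
- anti-proteinuria agents (7.1.4.5).

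The list should be fixed without reference to treatment arm. This matters here because SAP 7.1 keeps the study team blinded only unless futility is determined, and it was. Cases can then be flagged from the concomitant-medication data.

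If removal was intended, declare it in Section 10 and also report BICLA by the protocol definition.

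The cost is a short review of concomitant medications by indication and a possibly slightly lower BICLA rate. Protocol 7.8.2 lists therapy name, indication, dose, frequency and dates. It does not list route, which is needed to separate intra-articular from other corticosteroid. Route is probably recorded, since criterion 5 depends on IM and IV use, but this should be confirmed.
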